Day 1 — The second 12-hour urine collection will conclude at 7:00AM on day 1 and will be used to measure excretion of sodium and aldosterone. At 8:00AM, central blood pressure and vascular compliance will be assessed, followed at approximately 9:00AM by measurement of renal specific RAAS activity via para-aminohippurate (PAH) renal plasma flow testing with captopril, and systemic RAAS will be measured by plasma renin activity (PRA), angiotensin II (Ang II) and urine aldosterone. Next the subject will receive a mixed meal (10kcal/kg, 45% carbohydrate, 15% protein, 40% fat, 1g/kg glucose) to be consumed in 15 minutes with blood draws at 0, 10, 20, 30, 60, 90 and 120 minutes from the time the meal had begun to be consumed. The mixed meal will achieve glucose of 1g/kg by using specific amounts of a Trutol drink; the amounts are based on the subject’s weight, **Table 6**. Plasma glucose, insulin and c-peptide will be measured in all 7 samples of blood. Finally the participant will be fitted with a Spacelabs 90207 ambulatory BP monitor prior to discharge to be worn for 24-hours.

Food Description	Amount	Measure	Energy	Glucose (g)	Protein (%)	Fat (%)	Carbohydrate (%)
Whole milk, Hood	70	gram	44.49		21.05	47.37	31.58
Egg, whole	117	gram	174.33		34.45	62.18	3.37
Butter	7	gram	50.19		0.46	99.5	0.03
SF peanuts, dry roasted	30	gram	175.5		15.09	71.2	13.71
Turkey sausage	30	gram	46.68		42.56	53.85	3.59
Trutol, glucose drink	323	gram	327.52	81.72	0	0	100
Total			818.71	81.72	14.18	40.78	45.04

Follow-up — During the study, subjects will be phoned weekly by a study coordinator to assess for compliance and potential side effects. [name] will call all subjects every 2 weeks to discuss difficulties encountered with their new sleep schedule, to recommend improvements and encourage compliance with the protocol.

Parameters Measured: At the inpatient visits, the following measurements will be made:

Renal Specific RAAS — The activity of the local kidney RAAS can be measured by examining the change in effective renal plasma flow (RPF) after oral captopril while in high sodium balance. Effective RPF is measured as clearance of para-aminohippuric acid, because PAH is cleared solely and nearly entirely by the kidney. The protocol to measure PAH clearance is performed with the participant supine, **Figure 5**.

Systemic RAAS — PRA and ang II levels will be measured on the first morning blood draw.

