Biostatistical analysis

The primary purpose of the trial is to generate pilot data for a larger randomized control trial.

Therefore we aim to calculate means and standard errors for the parameters as well as estimates of effects of sleep extension and melatonin supplementation which will allow accurate power calculations and facilitate the design of a larger study. While we suspect we will be underpowered in this study to find significant differences in endpoints due to sleep extension or melatonin supplementation we will perform statistical analysis on the outcomes as follows. For the main outcomes (renal specific RAAS, BP, glycemic control [insulin sensitivity and β -islet cell function]), we can assume a normal approximation for the changes in log transformed endpoints and so will use an ANCOVA analysis to compare the change in outcome from baseline to 6 week follow-up between melatonin (N=8) and placebo groups (N=8) of the study. Finally we will test the interaction of sleep extension and melatonin supplementation using multivariable linear regression of the parameter change with predictors which will include treatment assignments (sleep extension and melatonin supplementation) and the interaction term **sleep extension *melatonin supplementation** in an analysis of all study participants (N=16).

For the purposes of this grant we have performed power calculations for sleep extension based on either pilot data from obese individuals from our own studies or published results.

Renal specific RAAS Activity – Based upon published data, we assume that change in renal specific RAAS activity ($\Delta\text{RPF}_{\text{captopril}}$) is $46\text{ml}/\text{min}/1.73\text{m}^2$ in obese individuals, SD 12^{72} , and From these values, we estimate that we will have 80% power to detect a change in $\Delta\text{RPF}_{\text{captopril}}$ with sleep extension of $15\text{ml}/\text{min}/1.73\text{m}^2$ (33% from baseline) with type I error of 0.05 (two-tailed), **Table 7**.

Central Blood Pressure – Based on pilot data, we assume a mean central systolic BP of 106 mmHg and SD 10 mmHg with a between measurement correlation coefficient 0.89. Thus, for ANCOVA analysis the SD is 6.0 for change in BP. From these values, we estimate we will have 80% power to detect a change in BP of 8 mmHg due to sleep extension with type I error of 0.05 (two-tailed), **Table 7**.

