24 hour Ambulatory Blood Pressure – Based on pilot data, we assume a mean 24-hour systolic BP of 122.8 mmHg and SD of 10.4mmHg with a between-measurement correlation coefficient 0.74. Thus for ANCOVA analysis the SD is 5.0 for change in BP. From these values, we estimate that we will have 80% power to detect a 6 mmHg change in 24-hour mean SBP due to sleep extension with a type I error rate of 0.05 (two-tailed).

Insulin sensitivity –Based on published data, we assume a mean insulin sensitivity of 19.03 dl/kg/min/pmol/l and SD of 1.38 dl/kg/min/pmol/l and a between-measurement correlation coefficient of 0.7.^{2,73} Thus for ANCOVA analysis the SD for change in insulin sensitivity is 1.1 dl/kg/min/pmol/l. From these values we estimate that we will have 80% power to detect a change in insulin sensitivity of 1.4 dl/kg/min/pmol/l due to sleep extension with type I error of 0.05 (two-tailed), **Table 7**

β -islet cell responsitivity – Based on published data, we assume a mean β islet cell response (dynamic response, ϕ_d) of 494.88 and SD of 25.16 and a assume a measurement correlation coefficient of 0.7.^{2,73} . Thus for ANCOVA analysis the SD for change in ϕ_d is 17.68. From these values we estimate that we will have 80% power to detect a change in β islet cell response of 24 due to sleep extension with type I error of 0.05 (two-tailed), **Table 7**. All power calculation performed with PS power and sample size calculator, version 3.0.34.

Table 7: Comparison of the change in outcome we are powered to detect compared with measured changes in outcomes detected in other studies with lifestyle interventions or BMI comparisons.

Outcome	Intervention/Comparison	Δ Measured	Detectable change in this study
Renal Specific RAAS ⁷²	Obese vs overweight	9ml/min/1.73m ²	15ml/min/1.73m ²
Central systolic BP ⁴⁶	Diet and exercise	12 mmHg	8mmHg
24hour ABPM ⁴⁷	Difference in BMI of 5kg/m ²	3 mmHg	6mmHg
Insulin Sensitivity ²²	Diet and exercise	19% change	7% change
β -islet cell function ⁴⁰	Diet	20% change	5% change

Risks and Discomforts

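### The stated 80% power for a 15 ml/min/1.73m² change in the renal RAAS response does not follow from the inputs printed with it

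*Combined protocol and SAP*

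**What the plan says.** All places are in the combined protocol and SAP.

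- **The measure.** Parameters Measured, Renal Specific RAAS, defines it within one visit, by "examining the change in effective renal plasma flow (RPF) after oral captopril while in high sodium balance".
- **The inputs.** Biostatistical analysis, Renal specific RAAS Activity, opens "Based upon published data, we assume that change in renal specific RAAS activity" and gives 46 ml/min/1.73m², SD 12, in obese individuals. The sentence then stops after a conjunction.
- **The claim.** The text resumes with "we estimate that we will have 80% power to detect a change in" the captopril response of 15 ml/min/1.73m² due to sleep extension, 33% of baseline, at two-sided 0.05. Table 7 prints 15 as detectable, beside a published contrast of 9 labelled "Obese vs overweight".
- **The analysis.** An ANCOVA on log-transformed endpoints will "compare the change in outcome from baseline to 6 week follow-up between melatonin (N=8) and placebo groups (N=8) of the study".
- **The other outcomes.** Each of the other four main-outcome paragraphs gives a one-visit SD, a between-measurement correlation (0.89, 0.74, 0.7, 0.7) and a separate SD for the ANCOVA, for example "Thus for ANCOVA analysis the SD for change in insulin sensitivity is 1.1 dl/kg/min/pmol/l".
- **Sample size.** The statistics section uses 8 per arm; Potential Benefits has 10 per arm.

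**The concern.** The mean of 46 is treated as a baseline level (15/46 = 32.6%, printed as 33%), so SD 12 belongs to the response at a single visit. The variable to be analysed is the change in that response over 6 weeks, adjusted for baseline. Its SD depends on how well the captopril response repeats between visits, and the renal paragraph prints nothing about that. As it stands, the power claim rests on SD 12 and an unstated N and test.

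Renal specific RAAS is the first main outcome listed, and the pilot is meant to support power calculations for a larger trial. A reader who takes 15 from Table 7 cannot tell which SD, correlation, test or sample size lies behind it.

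**Working it through.** **Inputs.** Difference 15, SD 12, two-sided 0.05 and 8 per arm (Biostatistical analysis); 10 per arm (Potential Benefits). The correlation r is not printed, so it is an assumed range. The SD is assumed equal at both visits.

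**1. Reproducing the 80%.** Enter SD 12 unchanged in a two-group comparison.

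- Normal approximation, power = Φ(15 / (12·√(2/n)) − 1.96):
  - n=8: 15/6.00 = 2.50, Φ(0.54) = 70.5%
  - n=10: 15/5.37 = 2.795, Φ(0.835) = 79.8%
- Noncentral t with 2n−2 df: 64.3% at n=8, 75.3% at n=10.
- Difference detectable with 80% power: 16.8 (normal) or 18.1 (t) at n=8; 15.03 (normal) or 15.9 (t) at n=10.

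The printed pair of 80% and 15 is recovered only with 10 per arm and a normal approximation. It is not recovered with the 8 per arm given in the same section.

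**2. A within-person reading.** The sentence is about sleep extension, so a before-after comparison was also tried. A paired t-test with SD 12 detects 13.9 (n=8), 12.0 (n=10), 9.0 (n=16) or 7.9 (n=20). None is 15.

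**3. The planned ANCOVA at 8 per arm.** Residual SD = 12·√(1−r²), noncentral t with 2n−3 = 13 df. The difference detectable with 80% power is about 1.516 × residual SD.

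| r (assumed) | Residual SD | Power for 15 | Detectable difference |
|---|---|---|---|
| 0 | 12.0 | 63.8% | 18.2 |
| 0.3 | 11.4 | 67.9% | 17.4 |
| 0.5 | 10.4 | 76.1% | 15.8 |
| 0.7 | 8.6 | 89.8% | 13.0 |
| 0.8 | 7.2 | 97.0% | 10.9 |

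For 80% power at 15 the residual SD must be 15/1.516 = 9.9, so r = √(1 − (9.9/12)²), about 0.57.

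**4. Unadjusted change score, for comparison.** SD = 12·√(2(1−r)), 14 df, 8 per arm. Power is 37.7% (r=0), 50.3% (0.3), 64.3% (0.5) and 85.1% (0.7). Here SD 12 is right only at r=0.5.

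**5. Was SD 12 entered as the change SD?** Detectable change divided by the stated ANCOVA SD is 8/6.0 = 1.33 (central systolic BP), 6/5.0 = 1.20 (24-hour BP), 1.4/1.1 = 1.27 (insulin sensitivity) and 24/17.68 = 1.36 (β-cell response). For renal RAAS, 15/12 = 1.25 falls inside that band. This suggests that it was, without proving it.

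**The case against.** Several points on the other side have force.

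- **The gap may be lost text.** The sentence breaks exactly where the other outcomes state a correlation. If an r of about 0.57 stood there, 15 at 8 per arm would be right. A reader might infer that the plan confuses the within-visit captopril change with the 6-week change and used the wrong SD. The documents do not show this: the paragraph separates a level of 46 from a change of 15 in it, and the use of SD 12 is inferred from ratios and one matching calculation. What stands is that the printed inputs do not give the printed result.
- **The direction is open.** With equal SDs at the two visits, SD 12 is an upper bound for the ANCOVA residual SD. Reading the statement as an over-claim is therefore not supported.
- **The Table 7 benchmark.** A reader might think that the correction decides whether 9 is within reach. For r from 0 to 0.8 at 8 per arm the detectable difference runs from 18.2 to 10.9 and always exceeds 9, as the printed 15 already does.
- **The other four rows are not a common standard.** It is tempting to call renal RAAS the one row out of line. But SD·√(1−r²) gives 4.6 for central systolic BP against a printed 6.0, and 7.0 for 24-hour BP against 5.0. Those rows state a correlation and an ANCOVA SD but do not share this derivation.
- **Little hangs on the figure.** The plan calls itself a pilot, expects to be underpowered, and will plan the larger trial from observed estimates. That limits the consequence. It does not supply a basis for the 80%.

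**Conclusion.** The renal RAAS power statement and its Table 7 entry are not supported by the inputs printed with them. With SD 12 and 8 per arm, power for 15 ml/min/1.73m² is 64% (t) or about 70% (normal), not 80%; with 10 per arm it is 75% or 80%. Under the planned ANCOVA at 8 per arm the answer depends on an unprinted correlation: 80% is reached from r of about 0.57, and the detectable difference lies between 18.2 (r=0) and 10.9 (r=0.8).

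These results assume equal SDs at both visits, no dropout and the raw scale; the plan analyses log-transformed endpoints, so they are indicative. They refer to the melatonin-placebo difference. The plan attributes its 15 to sleep extension, but every participant is asked to extend sleep and the planned ANCOVA has no group without it.

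**What to change.** In the renal paragraph of Biostatistical analysis:

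1. Label SD 12 as the one-visit SD of the captopril response and complete the broken sentence.
2. State the r, the residual-SD formula, the test and the N per arm. Write the formula out as SD·√(1−r²) and do not refer to the other outcomes for it.
3. Say that the figure is for the melatonin-placebo difference, and why.
4. Replace the 80% power claim for 15, and the Table 7 cell, with the detectable difference at 8 per arm: 18.2 (r=0), 15.8 (r=0.5), 13.0 (r=0.7), 10.9 (r=0.8). Present r as an assumed range unless the sponsor has repeat captopril RPF data to estimate it.
5. Note that these are raw-scale figures while the analysis is planned on the log scale.

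The cost is one paragraph and one table cell, with no added participants or procedures. The single figure becomes a range, and it is less favourable than 15 if the response repeats poorly.

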Pre-admission: All participants will wear a wrist activity monitor for a total of 8 weeks; 2 weeks prior to the baseline inpatient visit and for the 6 weeks between inpatient visits, **Figure 2**. They will complete a daily sleep log during the 2 weeks preceding the baseline visit and 6 weeks preceding second visit. Three days before admission, participants will be placed on a high salt diet by supplementing their usual diet with 150 mmol sodium/day for 3 days using dry bouillon added to food. All participants will also be asked to do a 24 hour diet recall for the day before admission.

Treatment assignments: Prior to admission for the baseline visit, **subjects will be randomized (1:1)** to receive study medication (melatonin 2mg of controlled release formulation or placebo). **All subjects will be asked to extend their sleep time by one hour** during the 6 week period between inpatient visits.

Baseline and Follow-up inpatient visit: Baseline and 6-week inpatient visits will be virtually identical. Each inpatient visit will begin at 4:00PM on Day 0 and end at 4:00PM on Day 1, **Figure 2**.

Figure 2: Schema for inpatient visit studies at 6-week visit.

Day 0 — We will complete two 12-hour urine collections for each subject. All subjects will begin the first 12-hour urine collection at their home at 7:00AM on day 0 of admission to the Brigham and Women’s Hospital Center for Clinical Investigation (CCI). The first 12-hour urine collection will be ended at 7:00PM that evening. The second 12-hour collection will begin and continued overnight until 7:00AM on day 1. The nurses will keep the daytime (7AM to 7PM) and nighttime (7PM to 7AM) urine separate to permit analysis of diurnal variation in urinary analytes. Subjects will fast after 9 pm to ensure a 12-hour fast by the next morning.

[figure not shown]

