Potential benefit to society: As described in detail in the **Study Procedure** section, we will perform a small pilot study of obese individuals. We plan to enroll a total of 20 individuals into a randomized controlled trial. All participants will be adults (age \geq 18 years), and will be recruited from the Boston area. Volunteers will be recruited and screened for inclusion based upon having a BMI \geq 30 kg/m², and having HbA1C between 5.7 and 6.4%. Other than having these “conditions”, potential participants will be expected to otherwise be in general good health, without severe co-morbid conditions as described in the **Subject Enrollment** section. There will be no involvement of special vulnerable populations. After randomization, participants will be retained by weekly phone calls; additionally, the duration of this trial (6 weeks) is relatively short. Study group assignment will be random, of the 20 participants, 10 will receive placebo, and 10 will receive controlled release melatonin (2.0mg of Circadin[®] nightly for 6 weeks). The 2 mg controlled-release formulation of melatonin has been studied previously in diabetic subjects and improves sleep duration. Pharmacokinetic data suggests that this dose of melatonin achieves nocturnal serum melatonin levels at or above physiological concentrations among healthy volunteers and is therefore adequate to replete nocturnal melatonin in individuals who have relatively low endogenous secretion.

The key potential benefit is the knowledge that is gained on potentially modifiable mediators of important pathophysiologic mechanisms of disease. The segment of the US population that would meet our study criteria is large; specifically, over half of the US adult population is obese, and nearly a quarter of these individuals have pre-diabetes. Thus, the results of this study could have profound public health implications.

Potential benefit to participants: It is possible that participants will gain direct benefit from these studies. First of all, it is possible that individuals who are not randomized to placebo will benefit from treatment. On the other hand, because this study is only 12-weeks in duration, these benefits (if present) will likely be short-lived.

Monitoring and quality assurance

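### The ANCOVA SDs for 24-hour SBP (5.0) and central SBP (6.0) do not follow from their stated inputs (7.0 and 4.6), and 6 mmHg has 61% power at 8 per arm even with SD 5.0 (36% with 7.0)

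*Combined protocol and SAP*

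**What the plan says.** The Biostatistical analysis section gives each BP outcome an SD and a correlation, then a derived SD, then a detectable change at 80% power and two-sided 0.05.

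- **24-hour SBP:** the inputs are "SD of 10.4mmHg with a between-measurement correlation coefficient 0.74". The derived value follows: "Thus for ANCOVA analysis the SD is 5.0 for change in BP". The claim is "we estimate that we will have 80% power to detect a 6 mmHg change in 24-hour mean SBP due to sleep extension".
- **Central SBP:** the inputs are "SD 10 mmHg with a between measurement correlation coefficient 0.89". The derived value follows: "Thus, for ANCOVA analysis the SD is 6.0 for change in BP". The claim is 80% power for 8 mmHg, again attributed to sleep extension.

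Table 7 lists 6 and 8 mmHg as what this study can detect. Neither paragraph states the N or the test behind its figure.

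The only ANCOVA described compares change "between melatonin (N=8) and placebo groups (N=8) of the study". Subject Enrollment also gives 16 participants, but Specific Aims gives 20, and Potential Benefits says "of the 20 participants, 10 will receive placebo, and 10 will receive controlled release melatonin". On sleep extension, the Treatment assignments paragraph says "All subjects will be asked to extend their sleep time by one hour".

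**The concern.** Both derived SDs are presented as consequences of the inputs just before them, and neither is. The 24-hour value is too small for its inputs and the central value is too large, so one rounding habit or one alternative formula cannot account for both.

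The power statement has a second problem that does not depend on the first. Even if SD 5.0 is accepted, the group sizes in the plan do not give 80% power for 6 mmHg in a two-arm comparison.

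The effect being powered is a third problem. Sleep extension has no comparator, so the design offers only an uncontrolled before-after change for it.

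The trial exists to support power calculations for a larger study. A reader who takes 5.0 mmHg as the planning SD when 7.0 is right would understate the required sample size by about half, since (6.995/5.0)² = 1.96.

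**Working it through.** **Inputs** (Biostatistical analysis): 24-hour SBP SD 10.4, r = 0.74, stated SD 5.0, effect 6 mmHg. Central SBP SD 10, r = 0.89, stated SD 6.0, effect 8 mmHg. Two-sided alpha 0.05. Arms of 8 (Biostatistical analysis) or 10 (Potential Benefits).

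**Step 1: the SDs.** The ANCOVA residual SD is SD × √(1 − r²). The change-score SD, with equal SDs at both visits, is SD × √(2(1 − r)).

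| | ANCOVA | Change score | Stated |
|---|---|---|---|
| 24-hour SBP | 10.4 × √(1 − 0.74²) = 6.995 | 10.4 × √(2 × 0.26) = 7.50 | 5.0 |
| Central SBP | 10 × √(1 − 0.89²) = 4.56 | 10 × √(2 × 0.11) = 4.69 | 6.0 |

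Under the ANCOVA formula, 5.0 would need r ≈ 0.88 and 6.0 would need r = 0.80. Two other expressions also fail: SD × √(1 − r) gives 5.30 and 3.32, and SD × (1 − r²) gives 4.71 and 2.08.

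Swapping the two correlations gives 10.4 × √(1 − 0.89²) = 4.74, near 5.0, and 10 × √(1 − 0.74²) = 6.73, not 6.0. A swap could explain only one of the two. By contrast, the insulin sensitivity paragraph can be recovered: 1.38 × √(2 × 0.3) = 1.07, stated as 1.1.

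**Step 2: power with the plan's own SDs.** I used a two-sample noncentral t with df = 2n − 2 and noncentrality Δ / (SD × √(2/n)).

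- 24-hour SBP, 8 per arm: 6 / (5.0 × √(2/8)) = 2.40, power 60.8%.
- 24-hour SBP, 10 per arm: 6 / (5.0 × √(2/10)) = 2.68, power 71.8%.
- 24-hour SBP, 12 per arm: power 80.2%. No document mentions 12 per arm.
- Central SBP, 8 per arm: 8 / (6.0 × √(2/8)) = 2.67, power 69.9%.
- Central SBP, 10 per arm: power 80.5%, which reproduces the claim.

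For 24-hour SBP with SD 5.0, one fewer degree of freedom for the covariate gives 60.3% at 8 per arm. A normal approximation gives 67.0% at 8 per arm and 76.5% at 10. None reaches 80%.

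**Step 3: power with the SDs that the inputs imply.**

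- 24-hour SBP, SD 6.995: 35.9% at 8 per arm and 44.3% at 10 per arm; 23 per arm are needed for 80%.
- Central SBP, SD 4.56: 90.3% at 8 per arm and 96.0% at 10 per arm.

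**Step 4: detectable differences at 80% power.** The standardised detectable difference is 1.507 at 8 per arm and 1.325 at 10 per arm. Multiplying by each SD gives, in mmHg (8 per arm / 10 per arm):

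| Assumption | 24-hour SBP (plan: 6) | Central SBP (plan: 8) |
|---|---|---|
| Stated inputs right (SD 6.995; 4.56) | 10.5 / 9.3 | 6.9 / 6.0 |
| Correlations swapped (SD 4.742; 6.726) | 7.1 / 6.3 | 10.1 / 8.9 |
| Stated SDs right (5.0; 6.0) | 7.5 / 6.6 | 9.0 / 8.0 |

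The 24-hour figure exceeds 6 mmHg in every row.

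**Step 5: the sleep-extension reading.** A one-sample t test of within-person change in all 16, at the change-score SD of 7.5, has 84.8% power for 6 mmHg and a detectable change of 5.6 mmHg. With the stated SDs and n = 8, a paired test detects 5.8 mmHg for 24-hour SBP, close to the plan's 6, but 6.9 mmHg for central SBP, not 8.

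**The case against.** The strongest reply is that the plan claims power for sleep extension, not for melatonin against placebo, so 61% and 36% score it on a contrast it did not name. On the one sleep-extension contrast the design offers, within-person change in 16 people, 6 mmHg is reached with 85% power even at SD 7.5. This is correct, and it has to be said alongside the headline figures. It does not rescue the paragraph. The plan ties its SD to an ANCOVA, and the only ANCOVA it describes is between the drug arms. A before-after change in everyone is uncontrolled. No paired reading considered above reproduces both BP figures.

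A second reply is that 10 per arm was probably used: central SBP then reproduces at 7.95 mmHg, and the 24-hour miss shrinks to 6.6 against 6. That is plausible, but the figure still misses, and the analysis section itself gives 8 per arm.

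Third, the practical effect is small. The plan expects to be underpowered, sets no sample size from these figures, and intends the larger trial to use estimates from this pilot's data. That stands, and it limits how much the error matters. It does not make the stated values correct, and Table 7 still presents them as this study's capability.

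Finally, the planned analysis uses log-transformed endpoints, while these calculations, like the plan's, are in mmHg. That is a limit on any replacement figure, but it does not explain the mismatch.

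**Conclusion.** The concern holds. The SD inconsistency depends on no choice of N, test or contrast: 10.4 with 0.74 gives 7.0 or 7.5, not 5.0, and 10 with 0.89 gives 4.6 or 4.7, not 6.0, assuming equal SDs at both visits. The documents do not show whether the inputs or the SDs are wrong.

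The power shortfall rests on reading the claim against the melatonin-placebo ANCOVA at two-sided 0.05. On that reading 6 mmHg has 61% power at SD 5.0 and 36% at SD 7.0 with 8 per arm, or 72% and 44% with 10 per arm. For central SBP the SD error works the other way: if its inputs are right, 8 mmHg has about 90% power at 8 per arm.

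This should be fixed, but it does not threaten the conduct of the pilot.

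**What to change.** 1. Go back to the pilot data, check the SDs and correlations for both BP outcomes, and correct either 5.0 and 6.0 or their inputs. Use one formula for both and name it.
2. For each calculation state the N, the test and the contrast, after settling whether the trial has 16 or 20 participants.
3. Restate the two BP paragraphs and their Table 7 rows as melatonin-versus-placebo differences detectable with 80% power. If the stated inputs prove right, these are 10.5 mmHg (8 per arm) or 9.3 mmHg (10 per arm) for 24-hour SBP, and 6.9 or 6.0 mmHg for central SBP. Say that they are on the mmHg scale while the analysis is of log-transformed endpoints.
4. Label any sleep-extension figure as an uncontrolled within-person change, with its own N.

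The cost is a recalculation and the rewording of two paragraphs and two table rows. The 24-hour figure becomes less favourable; the central figure improves if its inputs are right. No procedure, endpoint or visit changes.
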